### **7.3 Detection of Bias**

Any breaking of the blind for individual patients prior to formal unblinding will be documented in the clinical study report. Data collected after unblinding will be noted.

### **7.4 Outliers**

No formal outlier tests are planned. If necessary, values outside the pre-defined range, such as a WOMAC score not between zero and four, or a PGA score not between one and five, would be queried and excluded prior to database lock.

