6.1.2 Patient's Global Assessment of Disease Severity (PGA)

The PGA should be completed by patients at Screening, pre-dose Day 1 (prior to injection), and at Weeks 2, 4, 6, 8, 10, 12 and 24.

Patients are asked the following question: "Considering all the ways in which your arthritis affects you, please indicate how you are doing."

Patients respond by using a 5-point adjectival Likert score (0 = Very Well, 1 = Well, 2 = Fair, 3 = Poor, 4 = Very Poor).

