10.4.2 Secondary Endpoints

- Change in PGA between Baseline and Week 12
- Change in the 100 mm VAS Pain Scale between Baseline and Week 12
- Use of rescue analgesia (amount of acetaminophen used between Baseline and Week 12)
- Incidence and severity of treatment-emergent adverse events (TEAEs)

A serial gatekeeping approach will be used to test the secondary endpoints in a sequential manner (i.e. PGA, 100 mm VAS, rescue analgesia).

The difference between treatment groups in the mean change in PGA from Baseline to Week 12 will be analyzed using a similar MMRM model, with Treatment assignment, Week, and Baseline value as fixed effects and including patient as a repeated measure with a compound symmetric covariance matrix for residuals.

The difference between treatment groups in the mean change in 100 mm VAS from Baseline to Week 12 will be analyzed using a similar MMRM model, with Treatment assignment, and Baseline value as fixed effects and including patient as a repeated measure with a compound symmetric covariance matrix for residuals.

The difference between treatment groups in the amount of acetaminophen used between Baseline and Week 12 will be analyzed with a Wilcoxon rank-sum test.

All secondary efficacy analyses will be reported with one sided p-values and successively compared to a critical level of 0.025 if each preceding test was significant.

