### **3.4 Covariates**

Analyses of change will include treatment assignment, Week, and the Baseline measure of the variable being analyzed as a covariate in the model.

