## **7.2 Handling of Missing and Incomplete Data**

All data collected under this study protocol will be included in the assessment of patient safety. Missing or incomplete AE data will assume greatest relationship to study drug and/or severity. Incomplete adverse event and concomitant medication dates will be imputed as described in Section 12. If imputed dates are used, then they will be identified as such in the final study report. If an AE start date is missing or partially missing and no additional information is available from the site in order to establish whether the event started before or after the dose of study drug, the event will be considered to have started after dose. Partially missing dates where the month and year is prior to Day 0 will be classified as pre-dose.

For the co-primary effectiveness analysis of WOMAC pain change and WOMAC C function change, missing change scores will be imputed when the ITT analysis population is used. Missing data will be imputed by the fully conditional specification predictive mean matching multiple imputation approach of Berglund and Heeringa (2014). A sensitivity analysis will be conducted in which the missing 12-week endpoint is replaced by the Baseline WOMAC pain score.

For the secondary endpoints of PGA, 100mm VAS, and number of acetaminophen pills used, missing values will be imputed when the ITT analysis population is used. Imputation methods employed will be multiple imputation (SAS PROC MI and SAS PROC MIANALYZE) and single imputation methods (i.e., regression-based estimates, Baseline imputation, LOCF, and a worst/best case imputation).

Per the WOMAC User Guide, the patient's response will be regarded as invalid, and the subscale(s) deficient, in the event that two pain, both stiffness, or more than four physical function items are omitted. Further, if one pain, one stiffness, or 1-3 physical function units

are missing, the average value for the subscale will be substituted in lieu of the missing item value(s).

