### **8.6 Efficacy Analyses**

All efficacy variables will be assessed at Baseline (Day 0), Week 2, Week 4, Week 6, Week 8, Week 10, Week 12, and Week 24. Differences between treatments (Ampion and saline arms) will be presented using mean differences and 95% confidence intervals. Endpoints will be compared between Ampion and saline.

For summaries based on the PP, missing data will not be estimated or carried forward in any of the descriptive analyses. For summaries based on the ITT population, estimates from the MMRM will be shown incorporating imputed missing data via the full conditional specification method with predictive mean matching.

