### 8.6.2 Secondary Effectiveness Endpoints

Secondary effectiveness endpoints will be analyzed using the ITT and the PP analysis populations. All secondary efficacy tests will be performed and reported with one-sided p-values for superiority of Ampion.

Change from Baseline to 2, 4, 6, 8, 10, 12, and 24 weeks for the PGA will be analyzed using a MMRM model. Treatment assignment, Week, and Baseline PGA will be included as fixed effects and a compound symmetric covariance matrix for residuals to reflect the repeated measures.

Change from Baseline to 12 weeks for the 100mm VAS Pain Score will be analyzed using a MMRM model. Treatment assignment, and Baseline PGA will be included as fixed effects and a compound symmetric covariance matrix for residuals to reflect the repeated measures.

Use of rescue analgesia (amount of acetaminophen used) will be compared by treatment arm. A Wilcoxon rank-sum test will be used to compare overall pill count use over the study between saline and Ampion.

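### The SAP range-checks PGA at 1–5 although it is scored 0–4, adjusts VAS for Baseline PGA, and gives the gated PGA test no Week 12 contrast

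*SAP*

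**What the plan says.** **PGA range.** Protocol 6.1.2 scores PGA as "0 = Very Well, 1 = Well, 2 = Fair, 3 = Poor, 4 = Very Poor". SAP 7.4 states that, if necessary, "a PGA score not between one and five, would be queried and excluded prior to database lock". The same SAP sentence gives WOMAC a zero-to-four range, which matches its scale.

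**Missing PGA values.** For the secondary endpoints in the ITT population, SAP 7.2 lists multiple imputation and "single imputation methods (i.e., regression-based estimates, Baseline imputation, LOCF, and a worst/best case imputation"), without ranking them. SAP 8.6 says the ITT estimates come from the MMRM "incorporating imputed missing data via the full conditional specification method with predictive mean matching".

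**VAS covariate.** SAP 8.6.2 says of the VAS model: "Treatment assignment, and Baseline PGA will be included as fixed effects". SAP 3.4 calls for "the Baseline measure of the variable being analyzed as a covariate in the model". Protocol 10.4.2 describes the VAS model "with Treatment assignment, and Baseline value as fixed effects".

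**PGA model.** The gated endpoint is change in PGA from Baseline to Week 12 (SAP 3.2). SAP 8.6.2 fits changes at Weeks 2, 4, 6, 8, 10, 12 and 24 with treatment, week and Baseline PGA. Protocol 10.4.2 targets Week 12 "using a similar MMRM model, with Treatment assignment, Week, and Baseline value as fixed effects". Neither lists an interaction. The pain model in SAP 8.6.1 has treatment*week in both text and code. SAP 8.6.5 sends the exploratory PGA weeks, a list that omits Week 12, to the primary-analysis model.

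**Gate.** Under SAP 8.6.7, PGA is tested at one-sided 0.025 once both co-primaries succeed. VAS follows only if PGA succeeds, and rescue analgesia only if VAS succeeds.

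**The concern.** Each slip affects a test in the confirmatory sequence.

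- **Range.** A patient who truly answers 0 lies outside the written range, so the value goes missing because of what it is. If Ampion works, more 0s are lost in the Ampion arm, the difference tends to shrink, and the gate may close on a true benefit. Predictive mean matching cannot restore the 0s, because it draws only from observed values and none would remain.
- **VAS covariate.** Randomisation protects type I error. But precision is lost, and any chance imbalance in baseline VAS stays unadjusted.
- **PGA model.** Without the interaction, the model has one treatment difference common to all visits. The Week 12 difference is forced to equal it, so the gate can open on earlier weeks with no Week 12 effect, or miss an effect confined to Week 12. The same PGA data would also be analysed under two different models, one for the gated week and one for the exploratory weeks.

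**Working it through.** The documents give no PGA or VAS distribution or correlation. Every size below rests on stated assumptions.

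**(a) Range check**

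1. Scale {0,1,2,3,4} against check {1,2,3,4,5}: the valid score 0 is flagged and the impossible score 5 is accepted.
2. Hand example. Assume Week 12 percentages for scores 0–4 of 10/27/36/20/7 (Ampion) and 6/24/38/24/8 (saline).
   - All scores: means 1.87 and 2.04, difference −0.17.
   - Without 0s: 1.87/0.90 = 2.078 and 2.04/0.94 = 2.170, difference −0.092. That keeps 0.092/0.17 = 54%.
   - Two other assumed pairs (0s in 5% vs 3% and 18% vs 12%) keep 71% and 46%.
3. Simulation with baseline adjustment. Latent normal PGA with SD 1 is rounded to 0–4. Baseline mean is 2.6, saline mean at Weeks 2–12 is 1.5 to 2.25, and Ampion is 0.2 lower. Within-patient correlation is 0.4 or 0.6. All 0s are removed at every visit, and Week 12 change is analysed by ANCOVA on Baseline PGA. Week 12 0s then range from 6% vs 4% to 21% vs 16% (Ampion vs saline).

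| Handling of removed 0s | Shrinkage of PGA difference |
|---|---|
| No imputation | about 14–34% |
| Predictive mean matching, by arm | 17–33% |
| Predictive mean matching, arms pooled | 17–42% |
| Baseline imputation | 17–64% |

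4. Power without imputation. The ratio of effect to SE falls to 0.72–0.90 of its full value. A test with 90% power has effect/SE of 3.24. So 0.72 × 3.24 − 1.96 = 0.37, power 65%; and 0.90 × 3.24 − 1.96 = 0.96, power 83%.

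**(b) VAS covariate**

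Take unit variances. Let r be the correlation of baseline with Week 12 VAS, p that of Baseline PGA with baseline VAS, and assume that of Baseline PGA with Week 12 VAS is rp.

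- Residual variance of change adjusting for Baseline PGA: 2 − 2r − (rp − p)².
- Residual variance adjusting for baseline VAS: 1 − r².

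| r | p | Ratio |
|---|---|---|
| 0.3 | 0.3 | 1.3559/0.91 = 1.49 |
| 0.6 | 0.5 | 0.76/0.64 = 1.19 |
| 0.8 | 0.5 | 0.39/0.36 = 1.08 |

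The equivalent loss of patients for this test is 1 − 1/ratio, about 8% to 33%.

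**(c) PGA model**

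1. With complete data, compound symmetry and no interaction, the treatment term is the equally weighted mean of the visit differences. Week 12 carries 1/7, or 1/6 if PGA is not collected at Week 10, as the schedule tables in both documents show.
2. An effect of −0.20 at Week 12 only is estimated as −0.20/7 = −0.029.
3. Now take a benefit d at Weeks 2–10 and none at Weeks 12 and 24, with SD 1, 517 per arm and equal correlation ρ of 0.3–0.7. The mean effect is 5d/7 for k = 7 visits, or 4d/6 for k = 6. Adjusting for baseline, SE = √{(2/517) × [(1−ρ²) + (k−1)(ρ−ρ²)]/k}.
   - Example: d = 0.1, ρ = 0.5, k = 7 gives SE = √{(2/517) × 2.25/7} = 0.0353. Then 0.0714/0.0353 − 1.96 = 0.07, so the probability of a significant result is 53%.
   - d = 0.1 gives 46–63% across the grid; d = 0.2 gives 96–99%.
4. Gradual waning (−0.30, −0.30, −0.25, −0.20, −0.10, 0, 0): the model estimates −1.15/7 = −0.164. Using the SE without baseline adjustment, √{(2/517)(1+6ρ)/7}, it rejects with probability 99% at ρ = 0.3 and 86% at ρ = 0.7.

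**The case against.** - **The range check may never bite.** SAP 7.4 says values are excluded only if necessary and after a query. SAP 1 ties data review to the CRF categories. The CRF and the Data Management Plan are not available here. If the database stores PGA as 1–5, nothing is lost. This limits the size: the figures in (a) are for full application of the rule. It does not remove the conflict, because neither document mentions a recoding and a site that confirms a true 0 leaves it outside the written range.
- **Predictive mean matching is not the only method listed.** SAP 7.2 names PROC MI and several single imputations for PGA. Under a normal model, values below 1 can arise. This stands, so the statement that no 0 can be imputed holds only for the method in SAP 8.6. The repair would still be partial: in a rough check, only about 5–10% of imputed values fell below 0.5, although every removed value was a 0.
- **The 46–99% ignores the earlier gate.** PGA is tested only after pain and function both succeed at Week 12. This stands: the figure is the rejection probability of the PGA test alone, not the chance that the whole sequence opens wrongly.
- **The covariate lists are shorthand.** The WOMAC C paragraph in SAP 8.6.1 names only week, and Protocol 10.4.2 states Week 12 and a similar MMRM. The intention can be guessed. But the protocol's own primary models list no interaction either, so that reference does not supply one.
- **The VAS covariate is a copy slip.** Probably so. It still contradicts SAP 3.4 and the protocol for a gated test.
- **The sizes are unstable.** Without imputation, (a) ranges from 14–34% in the simulation to 29–54% under the hand-set distributions. They show direction and plausible scale, and are not predictions.

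**Conclusion.** All three points hold as written. The PGA range contradicts the protocol's scale, the VAS covariate contradicts SAP 3.4 and Protocol 10.4.2, and the gated PGA model does not test Week 12. The first can close the gate on a true benefit. The third can open it with no Week 12 effect, or miss an effect confined to Week 12. The second costs precision only.

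The sizes depend on the assumed distributions, correlations, SD of 1 and 517 patients per arm. Those for the range check also assume that every 0 is removed and that PGA is stored as 0–4. The co-primary analyses are untouched, so these are corrections that should be made rather than a threat to the trial's main conclusion.

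**What to change.** Make three wording changes to the SAP before unblinding:

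1. In SAP 7.4, set the valid PGA range to 0–4. If the database codes PGA as 1–5, document that coding and its mapping to the protocol scale instead.
2. In SAP 8.6.2, replace Baseline PGA with baseline VAS in the VAS model.
3. In SAP 8.6.2, add treatment*week to the PGA model and state that the gated test is the Week 12 treatment contrast.

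The cost is the SAP text; no new data are needed. Made after unblinding, the same changes could look driven by the results.

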### **7.5 Testing/Validation Plan**

All statistical analyses will be programmed using SAS® software version 9.3, or later. Graphic displays may be produced using R, version 3.0.0, or later. Standard macros will be used in programming when possible. Testing and validation plans for all programs will be developed in accordance with contract research organization guidelines and will include independent programming of tables and analyses.

## **8. STATISTICAL METHODS OF ANALYSIS**

### **8.1 General Principles**

Data will be summarized by saline and Ampion arms. Descriptive statistics on continuous variables will include mean, standard deviation, median, 25th and 75th percentiles, and range. Change from Baseline will include a 95% confidence interval. Categorical variables will be summarized using frequency counts and percentages. Data listings of individual patient's data will be provided.

Statistical testing for the primary endpoints of pain and function will be performed using a one-sided p-value compared to  $\alpha=0.025$ .

Other efficacy analyses will be presented with one-sided p-values. Safety analyses will be presented as two-sided.

### **8.2 Patient Accountability**

The number of patients who are randomized, receive study drug, and complete the study will be summarized. The number of patients included in the safety, ITT, and PP analysis sets will be included in the table. Attendance at each visit, including missed visits, discontinuations, lost to follow-up, and percentage accountability will be summarized. A list of patients who withdraw early will be provided. It will include the reason and timing of the withdrawal. Similarly, the reason any patient is excluded from an analysis set will also be provided. In addition, significant known protocol deviations will be noted for individual patients; a summary table may also be provided.

### **8.3 Demographic and Baseline Characteristics**

Age, race, ethnicity, sex, height, weight, and Baseline measures of WOMAC and PGA will be summarized by treatment arm for all patients randomized, using descriptive statistics.

### **8.4 Safety Analyses**

The safety profile will be based on adverse events, concomitant medications, vital signs, and results of physical examination. All treated patients will be included in the safety analyses.

### **8.5 Adverse Events**

Adverse events will be grouped by system organ class and by preferred term within system organ class according to the latest version of the MedDRA coding dictionary. The number of patients reporting at least one adverse event and each adverse event will be summarized treatment group. Tables and/or narratives of any on-study death, serious or significant adverse events, including early withdrawals because of adverse events, will be provided should they occur.

#### **8.5.1 Concomitant Medications**

The number and percent of patients receiving concomitant medications or treatments prior to and during the study and at the final visit will be tabulated and presented overall and by treatment group for the Safety analysis dataset. Concomitant medications, using the generic medicine name, and treatments will be summarized using descriptive statistics and will be presented by type of drug (WHO drug classification preferred term and Anatomical Therapeutic Chemical Classification [ATC] Level 1) by treatment group.

#### **8.5.2 Vital Signs**

Vital signs will be listed for each patient. These will include temperature, respiration, pulse, and blood pressure. Summaries over time and changes from Baseline will be provided.

#### **8.5.3 Physical Examinations**

Any new or abnormal findings will be recorded as adverse events. Status of each body system will be summarized at each visit.

### **8.6 Efficacy Analyses**

All efficacy variables will be assessed at Baseline (Day 0), Week 2, Week 4, Week 6, Week 8, Week 10, Week 12, and Week 24. Differences between treatments (Ampion and saline arms) will be presented using mean differences and 95% confidence intervals. Endpoints will be compared between Ampion and saline.

For summaries based on the PP, missing data will not be estimated or carried forward in any of the descriptive analyses. For summaries based on the ITT population, estimates from the MMRM will be shown incorporating imputed missing data via the full conditional specification method with predictive mean matching.

### 8.6.1 Primary Effectiveness Endpoints

Change in WOMAC A pain score as measured by a 5-point Likert scale, from Baseline to Week 12, will be analyzed by including change from Baseline at 2, 4, 6, 8, 10, and 12 weeks in a mixed-effects model with repeated measures (MMRM). Treatment assignment Week, the treatment\*week interaction and Baseline WOMAC pain score will be included as fixed effects. Patient ID will be included to denote repeated measures and a compound symmetric covariance matrix will be used for residuals. Least squares means and treatment difference with 95% confidence intervals will be presented.

SAS code used will follow the following format:

```
Proc mixed;
  Class PtID treatment week;
  Model delta_pain = treatment baseline_pain week treatment*week;
  Repeated week / subject=newID type = CS;
  Lsmeans active*week / SLICE=week diff;
run;
```

The primary analysis will include the repeated measures of WOMAC C function sub score from Baseline to Weeks 2, 4, 6, 8, 10, and 12 and will use a mixed-effects model with repeated measures MMRM model, with Week as a fixed effect, and including patient ID as a repeated measure with a compound symmetric covariance matrix for residuals.

The primary effectiveness endpoints will be analyzed using the ITT analysis population. In order to preserve the randomization, any missing values at 12 weeks will be imputed. Week 12 visit data collected more than 14 days after the target day of 84 will be used and not imputed. The primary method of imputation will be the full conditional specification method with predictive means matching (Berglund & Heeringa 2014). This imputation method uses all observed values of the primary outcome at Baseline, 2, 4, 6, 8, 10, and 12 weeks to impute an individual's missing values. To determine the possible effect of missing data on the primary analysis, the following sensitivity analyses will be performed: 1 – multiple imputation (SAS PROC MI, using the default method MCMC along with PROC MIANALYZE); 2 – last observation carried forward (LOCF) 3 – a regression-based prediction using individual's prior data and time of prior data will be used to impute Week 12 data; and 4 – a conservative imputation approach will be performed where the greatest pain reduction observed in the study will be imputed for the saline arm and the worst change in pain score observed in the study will be used to impute missing 12-week values in the Ampion arm. Any imputed value that results in more than one decimal place will be rounded to one decimal place.

An analysis of site effect will be performed. If the main effect has a p-value of 0.15 or smaller in a secondary analysis, site will be included in the model and summaries of the primary effectiveness endpoint will be produced by site as well as pooled over sites.

WOMAC A Pain scores and the WOMAC C functions scores and their respective change and percent change from Baseline will be summarized by visit. The Change from Baseline scores will include a 95% CI. For the WOMAC A Pain subscore and WOMAC C Function subscore, a test for the main effect for Ampion vs. saline will be included on the summary tables at weeks indicated as primary or secondary endpoints.

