5.1.5 Visit 3 (Week 2 ± 7 days, telephone contact)

The following procedures will be performed:

- Perform WOMAC and PGA evaluations of the study knee
- Record AEs
- Record concomitant medications
- Review rescue medication use

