6.1.1 WOMAC® Osteoarthritis Index ([Bellamy 1988](#))

The clinical effects of treatment on OA pain and function will be evaluated during clinic visits at 6, 12, and 24 weeks, and telephone contacts at 2, 4, 8 and 10 weeks, using the WOMAC Index

3.1, and the PGA. All patients are required to take at least five minutes to complete the questionnaire.

Patients are asked about their pain, stiffness, and function in the knee (study joint) due to arthritis during the last 24 hours.

In addition to WOMAC scoring during clinic visits, daily WOMAC A pain sub scores will be collected for seven days up to and including Baseline and Week 12 to allow for calculation of WOMAC A weekly pain scores, which will be used for conducting the primary efficacy analysis.

Patients respond to each subscale by using a 5-point adjectival Likert score (0 = None, 1 = Mild, 2 = Moderate, 3 = Severe, 4 = Extreme) and 100mm VAS.

The WOMAC B and WOMAC C sub scores will be collected at Weeks 0 (Baseline), 2, 4, 6, 8, 10, 12, and 24 using the 5-point Likert scale. Patients respond to each subscale by using a 5-point adjectival Likert score (0 = None, 1 = Mild, 2 = Moderate, 3 = Severe, 4 = Extreme).

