10.3.6 Definition of Study Visits

This clinical trial has a total of 11 study visits, including telephone contacts, during the 24-week study (see Table 6.1). The time-on-study for each patient observation will be defined relative to Day 0, the day of the initial dose. For analysis, the Baseline measure is the latest measure prior to initiation of treatment. For analysis of Baseline WOMAC A pain, the Baseline pain score is the average of all scores measured during days -6 to 0, prior to injection of treatment. For analysis of Week 12 WOMAC A pain, the Week 12 pain score is the average of all scores measured during the seven days prior to and including the Week 12 office visit.

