### **2.4 Sample Size**

This trial will use an adaptive design with promising zone method for sample size re-estimation.

This trial is designed for 1,034 patients, 517 per study arm, randomized 1:1 for Ampion and saline IA injection. There will be an interim analysis when at 724 patients, 362 per study arm, have completed their Week 12 visit.

A promising zone analysis will be performed at the interim. Following the interim analysis, enrollment will either a) continue up to a total of 1034 patients, 517 patients per study arm, randomized 1:1 for Ampion and saline IA injection; b) allow for sample size re-estimation up to a maximum of 1.5 times the original trial size for a total of 1,552 patients, 776 per study arm, randomized 1:1 for Ampion and saline IA injection.

The Ampion effect was estimated as the average change in pain from Baseline to Week 12 for KL 4 subjects receiving Ampion from all prior single injection studies randomized 1:1 with saline control. Saline effect was estimated as the average change in pain from Baseline to Week 12 for KL 4 subjects receiving saline from all prior single injection studies randomized 1:1 for Ampion and saline. The sample size for assessing the WOMAC A Pain score alone would be 690 total patients for 90% power.

The Ampion effect was estimated as the average change in function from Baseline to Week 12 for KL 4 subjects receiving Ampion from all prior single injection studies randomized 1:1 with saline control. Saline effect was estimated as the average change in function from Baseline to Week 12 for KL 4 subjects receiving saline from all prior single injection

studies randomized 1:1 for Ampion and saline. The sample size for assessing the WOMAC C Function score alone would be 984 patients for 90% power.

The total sample size is chosen as the larger of the two values. To be conservative sample sizes were estimated with a 5% dropout so 1,034 patients will be enrolled to achieve 984 total patients. All ITT patients will be included in the statistical analysis. At the assumed effect size there is a 90% probability of success at 1,034 patients.

The study design of 1,034 total patients achieves 97% power assuming a WOMAC A pain score with mean pain decreases of -0.83 for Ampion and -0.62 for saline and a standard deviation of 0.85.

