### **3. STUDY ENDPOINTS AND COVARIATES**

#### **3.1 Primary Endpoints**

The trial will test whether Ampion can produce a superior improvement in pain vs. saline control and a superior improvement in function vs. saline. This goal is achieved using two co-primary endpoints:

Change in the WOMAC A weekly pain sub score between Baseline and Week 12  
Change in WOMAC C physical function sub score between Baseline and Week 12

An average of the daily WOMAC A pain assessments will be used to calculate the weekly pain score, at baseline and at Week 12.

Mean 12-week change in the WOMAC A pain score will be compared between Ampion and saline control. Mean 12-week change in WOMAC C physical function score will be compared between Ampion and saline control.

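### The SAP's pain model gives the seven-day Week 12 diary mean the same variance as the single readings at Weeks 2–10, so the stated 0.025 level of the Week 12 pain test is not assured (minor)

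*SAP*

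**What the plan says.** SAP 8.6.1 fits change in WOMAC A at Weeks 2, 4, 6, 8, 10 and 12. The code line is "Model delta_pain = treatment baseline_pain week treatment*week", with `type = CS` on the repeated statement and least-squares means compared within week. The text matches the code: "Patient ID will be included to denote repeated measures and a compound symmetric covariance matrix will be used for residuals".

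The six values are not the same kind of measurement:
- **Week 12.** Protocol 6.1.1 says that "daily WOMAC A pain sub scores will be collected for seven days up to and including Baseline and Week 12". Protocol 10.3.6 adds that "the Week 12 pain score is the average of all scores measured during the seven days prior to and including" the clinic visit. SAP 3.1 agrees: "An average of the daily WOMAC A pain assessments will be used to calculate the weekly pain score, at baseline and at Week 12".
- **Weeks 2 to 10.** Protocol 5.1.5 to 5.1.9 ask for one evaluation per contact: "Perform WOMAC and PGA evaluations of the study knee". The schedule of assessments has no diary at these visits.

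Neither document plans a robust SE, a heterogeneous or unstructured covariance, or a sensitivity analysis on the covariance. The list in SAP 8.6.1 opens with "To determine the possible effect of missing data on the primary analysis, the following sensitivity analyses will be performed" and deals only with imputation. SAP 8.6.4 deals with the per-protocol set.

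Protocol 10.3.4 and 10.4.1 also specify compound symmetry for pain, but list treatment, week and baseline without treatment-by-week. SAP 3.4 lists the same three terms.

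**The concern.** A mean of several daily scores varies less than one score unless the days are perfectly correlated. The schedule therefore makes the Week 12 measurement different from the other five, and the model then assumes that all six have equal variance.

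With treatment-by-week in the model and near-complete data after imputation, the estimated Week 12 difference is in effect the baseline-adjusted difference in Week 12 means. Its true sampling variance is the Week 12 variance, but the SE that the model reports uses the average variance over six visits. The two agree only if the Week 12 variance equals that average. The Baseline diary mean is subtracted at every visit, so it does not create the inequality.

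At stake are the SE, confidence interval and p-value of one of the two tests that decide the trial.

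**Working it through.** **Inputs.** From the documents: one-sided level 0.025; six visits; 1,034 enrolled and 984 after dropout; and, from SAP 2.4, "mean pain decreases of -0.83 for Ampion and -0.62 for saline and a standard deviation of 0.85", a difference of 0.21. The documents do not say whether 0.85 refers to a single reading or a diary mean. They give no SD by visit, no day-to-day SD (d) and no day-to-day autocorrelation (ρ), so these are assumed and varied. I take 0.85 as the residual SD, treat the data as complete and ignore between-imputation variance.

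**The plan's own figures.** Total N for 90% power = 4 × (1.960 + 1.282)² × 0.7225 / 0.0441 = 688.6, or 345 per arm, 690 in total, as stated. Power is 97.8% at 1,034 and 97.2% at 984, consistent with the stated 97%. The reference below is 97.2%.

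**Formulas.**
- SE ratio r = √(mean of the six visit variances / Week 12 variance)
- Actual level = 1 − Φ(1.96 r)
- True SE = √(4 × Week 12 variance / 984)
- Power = Φ(0.21 / true SE − 1.96 r); with a correct SE, put r = 1
- Diary averaging lowers the Week 12 variance by d²(1 − f). For seven days f = (1/49) ΣΣ ρ^|i−j|, which is 0.143, 0.348 and 0.798 for ρ = 0, 0.5 and 0.9.

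**Case 1: 0.85 is a single-reading SD and underlying variance is equal at all visits.** Example with d = 0.4, ρ = 0: Week 12 variance = 0.7225 − 0.16 × 6/7 = 0.5854. Mean variance = (5 × 0.7225 + 0.5854)/6 = 0.6996. So r = 1.093 and level = 1 − Φ(2.143) = 0.016. True SE = 0.0488, so power = Φ(4.305 − 2.143) = 98.5%, against 99.0% with a correct SE.

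| ρ | SE too large by (d = 0.3 / 0.4 / 0.5) | Actual level |
|---|---|---|
| 0 | 5% / 9% / 16% | 0.020 / 0.016 / 0.011 |
| 0.5 | 4% / 7% / 11% | 0.021 / 0.018 / 0.014 |
| 0.9 | 1% / 2% / 3% | 0.024 / 0.023 / 0.022 |

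Power for ρ = 0 is 98.0 / 98.5 / 99.0%, against 98.4 / 99.0 / 99.6% with a correct SE. All are above 97.2%. If only three of the seven days are scored (ρ = 0), the SE is 4–12% too large.

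A simulation of this case for ρ = 0 (492 per arm, latent correlation 0.7, 10,000 null trials, Monte Carlo SE about 0.001 to 0.0016) gave these levels for d = 0.3 / 0.4 / 0.5:
- Compound symmetry with the interaction: 0.020 / 0.014 / 0.011
- Week 12 with its own variance: 0.025 / 0.024 / 0.023
- Compound symmetry without the interaction: 0.026 / 0.024 / 0.024

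**Case 2: 0.85 is the Week 12 diary SD (ρ = 0).** The single-reading SD is then 0.894 / 0.927 / 0.968 and r = 1.044 / 1.076 / 1.117. The level is 0.020 / 0.018 / 0.014, and power 96.6 / 96.1 / 95.4% against 97.2%.

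**Case 3: the single-reading SD also grows linearly to 0.85 at Week 12 (ρ = 0).** Entries are r (level).

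| SD at Week 2 | d = 0.3 | d = 0.4 | d = 0.5 |
|---|---|---|---|
| 0.75 | 0.987 (0.0266) | 1.028 (0.0220) | 1.092 (0.0162) |
| 0.70 | 0.957 (0.0304) | 0.996 (0.0255) | 1.057 (0.0192) |
| 0.65 | 0.927 (0.0347) | 0.964 (0.0294) | 1.023 (0.0225) |

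Five of the nine levels lie above 0.025. The two effects cancel at a Week 2 SD of 0.77, 0.71 or 0.62 for d = 0.3, 0.4 or 0.5.

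**The case against.** **The direction is not fixed.** A reader might infer that the pain test runs below 0.025, or, from Case 3, that it inflates false positives. The documents support neither as a prediction. The first needs equal underlying variance at all visits; the second needs variance that grows over time. The documents neither state nor exclude either. This objection stands, and the conclusion is therefore only that the level is not assured.

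**The larger figures need independent days.** Consecutive daily pain scores may well be correlated, and at ρ = 0.9 the level is close to nominal. Even with independent days, d = 0.2 gives 0.0227. This stands as a limit on size. Under equal underlying variance the sign does not change.

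**The consequence is small.** Pain alone needs 690 patients, and the trial is sized on function. This stands and sets the severity.

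**The error is in only one of the model statements.** The protocol models and SAP 3.4 have no interaction, SAP 8.6.1 also mentions a main-effect test for its summary tables, and the simulation shows no such error without the interaction. This stands, and it puts the choice of estimator first. It does not clear the SAP's code, which is the most specific statement of the primary analysis.

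**Unequal variances would be visible.** By-visit summaries will include SDs and 95% intervals. That is true, but it does not correct the primary test.

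**Conclusion.** The point holds as a minor one. In the SAP's WOMAC A model with treatment-by-week, the Week 12 SE rests on an equal-variance assumption that the measurement scheme gives reason to doubt, and nothing planned checks or corrects it.

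On the diary averaging alone the test is conservative, by an amount that depends on quantities the documents do not give. Growth of variance over visits could cancel or reverse this. If 0.85 is a single-reading SD there is no shortfall against the planned pain power. If it is the Week 12 diary SD, the loss is 0.6 to 1.8 points with independent days.

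A reader might extend the point to WOMAC C because it is also modelled with compound symmetry. The documents do not support that on this ground: WOMAC C has no diary mean, so this mechanism is absent, and no error is claimed for it or for the interim analysis based on it.

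**What to change.** Before unblinding at the interim:

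1. State one Week 12 estimator for WOMAC A. Protocol 10.3.4 and 10.4.1, SAP 3.4 and SAP 8.6.1 should agree on whether treatment-by-week is in the model and on the Week 12 contrast that is tested.
2. Replace `type = CS` in that model with a covariance that gives Week 12 its own variance. Unstructured is the natural choice, with a named fallback for non-convergence, such as a heterogeneous structure with a sandwich SE. A heterogeneous structure or a robust SE alone would also remove this error.

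No change to WOMAC C is asked for on this ground.

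The cost is a code option and a sentence in the SAP, with no new data. An unstructured matrix for six visits has 6 × 7 / 2 = 21 parameters instead of 2, which about 984 patients support. Aligning the protocol needs a written amendment under Protocol 11.3. Protocol 10.3.10 already foresees a final SAP before the interim unblinding, so the SAP change fits there.
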